### 5.12.1.3. Stopping and holding rules

If any Grade 4 dermatological event occurs, lapatinib must be permanently discontinued.

#### 5.12.1.3.1. Holding rule

Lapatinib should be held for 14 days, in all patients who experience either a grade 3 dermatological reaction or a grade 2 dermatological reaction, which is unimproved after two-weeks of medical management. After the 14 day interruption, and provided the dermatological reaction improves to grade 1 or better, lapatinib may be restarted at the previous dose.

If the investigator considers continuation of lapatinib without interruption, it is required that he/she discusses the individual case with the GSK medical monitor before taking any decision on study treatment. In some cases, resolution of grade 2 or greater dermatological reactions occurred without interruption of lapatinib. For those subjects

that interrupted lapatinib, many were able to resume lapatinib therapy at the same dose after resolution of the dermatological event.

#### **5.12.1.3.2. Re-challenge**

One re-challenge may be considered, if indicated in the opinion of the investigator, for subjects who present with NCI-CTCAE Grade 3 dermatological events which recover to NCI-CTCAE Grade 1 or better (within 14 days) after holding lapatinib.

#### **5.12.1.3.3. Stopping rules**

Lapatinib must be permanently discontinued for:

- Recurrent Grade 3 dermatological reactions
- All Grade 4 dermatological reactions, including Stevens-Johnson Syndrome and Toxic Epidermal Necrolysis.

#### **5.12.1.4. Treatment**

There is no standard treatment proven to be effective for lapatinib-induced dermatological reactions. Therefore it is recommended that subjects who develop Grade 2 dermatological reactions that are unresponsive to initial treatment may be referred to a dermatologist for evaluation and management. For subjects with Grade 3 or 4 dermatologic events, or chronic, persistent or recurring lower grade skin events, a dermatology consultation is strongly encouraged.

There are some general precautions for subjects receiving lapatinib therapy. Subjects are recommended to avoid exposure to bright sunlight. When going out into bright sunlight, a broad spectrum sunscreen (containing titanium dioxide or zinc oxide) with an SPF of at least 30 should be applied.

A variety of agents may be used to manage dermatological reactions. These include mild-to-moderate strength steroid creams, topical or systemic antibiotics, topical or systemic antihistamines, immunomodulators, hypoallergenic moisturisers, and emollients.

The need for oral or topical antibiotics and topical steroids is a clinical decision. For **pruritic** lesions oral antihistamine agents may be effective. For **paronychia** antiseptic bath and local potent corticosteroids in addition to tetracycline therapy is recommended. If no improvement occurs, a dermatology or surgery consultation is recommended. For **infected** lesions appropriate, culture driven treatment with systemic or topical antibiotics is recommended as clinically indicated.

Oral retinoids are not recommended because of theoretical concerns about negative effects on lapatinib's mechanism of action. Topical steroids may result in skin irritation and severe xerodermia (dryness). Oral steroids may be used for a short treatment course (maximum of 14 days).

## 5.12.2. Gastrointestinal Events

If gastrointestinal AEs are not appropriately managed, they may be associated with the development of dehydration.

### 5.12.2.1. Nausea and vomiting

In subjects who vomit and are unable to retain lapatinib and/or capecitabine, every attempt should be made to control nausea and vomiting. If a subject vomits after administration of study drug, the subject should be instructed not to retake the dose. Subjects should take the next dose as scheduled. If vomiting persists, then the subject should contact the investigator.

### 5.12.2.2. Diarrhoea

Diarrhoea is the primary efficacy endpoint of this study. It is essential that the investigator understands fully the classification of diarrhoea and the definitions of severity used in this study (Table 8). For each diarrhoea AE report, the investigator should assess the change in stool form and frequency relative to the normal form and frequency for the subject to accurately ascertain the grade of the diarrhoea AE.

In rare cases, diarrhoea can be debilitating, and potentially life threatening if accompanied by dehydration, renal insufficiency, and/or electrolyte imbalances. Diarrhoea should be managed proactively to avoid complications such as dehydration, renal insufficiency, and electrolyte imbalances or worsening of the subject's condition.

Standardised guidelines for treating chemotherapy-associated diarrhoea have been developed by ASCO [Benson, 2004], and these have been used to develop specific guidelines for the management of diarrhoea associated with lapatinib use (Appendix 1). These guidelines should be used in combination with the treatment delay and dose reduction rules described in Section 5.10 and in Section 5.11.

## 5.12.3. Cardiac and Respiratory Events

### Asymptomatic Cardiac Events

Subjects who have a  $\geq 20\%$  decrease in left ventricular cardiac ejection fraction relative to baseline, and an ejection fraction below the institution's lower limit of the normal range (LLN), should have a repeat evaluation of ejection fraction 1-2 weeks later while still receiving treatment with lapatinib and capecitabine.

If the repeat ejection fraction evaluation confirms a  $\geq 20\%$  decrease in left ventricular cardiac ejection fraction, and the ejection fraction is below the institution's LLN, then treatment with lapatinib and capecitabine should be temporarily discontinued.

If the left ventricular ejection fraction recovers during the next 3 weeks, after consultation and approval of the medical monitor, the subject may be restarted on treatment with lapatinib and capecitabine at a reduced dose of lapatinib. For such subjects, monitoring of left ventricular ejection fraction will then be performed 2 weeks and 4 weeks after rechallenge, and then every 4 weeks thereafter.

If repeat ejection fraction evaluation still shows a  $\geq 20\%$  decrease in left ventricular ejection fraction relative to baseline, and the value is below the institution's LLN, then the subject should be withdrawn from treatment with lapatinib and capecitabine.

### Symptomatic Respiratory and Cardiac Events

Subjects should be monitored for symptoms of pulmonary toxicity (dyspnoea, cough, fever, interstitial pneumonitis) or cardiotoxicity, and subjects who experience pulmonary symptoms or left ventricular systolic dysfunction which are NCI CTCAE Grade 3 or greater must be withdrawn from treatment with lapatinib and capecitabine.

#### 5.12.4. Hand and Foot Syndrome

The frequency of hand and foot syndrome among patients receiving capecitabine has led the US regulatory agency, in conjunction with the manufacturer, to arrive at the capecitabine-specific toxicity rating scale shown in [Table 14](#).

**Table 14** Hand and Foot toxicity rating scale

Criteria for grading palmar-plantar erythrodysesthesia (hand and foot) syndrome	
Toxicity Grade	Manifestations
Grade 1	Numbness, dysesthesia/paresthesia, tingling, painless swelling, or erythema of the hands and/or feet that causes discomfort but does not disrupt normal activities of daily living
Grade 2	Painful erythema and swelling of the hands and/or feet that results in discomfort affecting normal activities of daily living
Grade 3	Moist desquamation, ulceration, blistering, and severe pain of the hands and/or feet and/or severe discomfort that causes inability to work or perform activities of daily living
Source: Capecitabine SPC	

In the event the subject presents with hand-foot syndrome, follow the recommended dose modification guidelines for capecitabine described in Section 5.11. If Grade 2 or 3 hand-foot syndrome occurs, administration of lapatinib and capecitabine should be stopped until resolution to Grade 0-1.

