## 5.9. Dose Adjustment

Dose adjustment will be considered for lapatinib (Section 5.10) and capecitabine (Section 5.11), and the dose of either agent may be adjusted independently of the other. All subjects who may require discontinuation of either lapatinib or capecitabine must discontinue both treatments. Subjects should be carefully instructed when any dose modifications occur.

Treatment with lapatinib and capecitabine may be delayed up to 2 weeks, to allow for resolution of toxicity except in the event of a  $\geq$  Grade 3 relative decrease in left ventricular ejection fraction, interstitial pneumonitis or hepatotoxicity. Guidelines for the management of these events are presented in Section 5.12.3 (cardiovascular and respiratory) and Section 5.13 (hepatobiliary).

No dose reduction or dose delay is permitted for octreotide. Subjects who show intolerance to the s.c. injection of octreotide must not receive treatment with octreotide LAR. Episodes of mild diarrhoea which occur following the first dose of octreotide LAR and prior to the first dose of lapatinib and capecitabine should be managed in accordance with the diarrhoea management guidelines (Appendix 1). The use of octreotide in the s.c. formulation for the management of diarrhoea refractory to treatment with loperamide is not excluded. Investigators should use their clinical judgement concerning the use of octreotide s.c. in subjects randomised to receive treatment with octreotide LAR, particularly during Week 2 through to Week 12 of treatment with lapatinib and capecitabine, when circulating concentrations of octreotide should already be within the clinically effective range.

Subjects who report constipation with a severity of NCI CTCAE Grade 2 and above (Table 9) or other adverse events which are considered likely to be related to octreotide treatment following the first dose of octreotide LAR must not receive the second dose of octreotide LAR.

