**Table 10 Dose modification rules for lapatinib**

Toxicity NCI-CTCAE Grade	During Course of Therapy	Lapatinib Dose Change
Grade 1	Maintain dose	No change
Specific Events of Grade 2/3 Haematology Absolute Neutrophil Count (ANC) <1.5 × 10  /L Platelet count is <100.0 × 10  /L Haemoglobin is <9.0 g/dL (after transfusion if needed) Chemistry For liver AE refer to Section 5.13 Serum Creatinine ≥1.5 mg/dL Calculated Creatinine Clearance <40mL/mins (Appendix 6)	Interrupt treatment until resolved to Grade 0-1, up to 14 days.  If toxicity does not resolve, consult GSK Medical Monitor to determine if it is in the best interest of the subject to continue in the study	1 st appearance Resume 100%  2 nd appearance Resume 100% or dose reduce to 1000mg/day.  3 rd appearance-Resume 100% or dose reduce to 1000mg/day.
Grade 2-Any other event For Cardiac Ejection Fraction and interstitial pneumonitis AEs, refer to Section 5.12.3. For liver AE refer to Section 5.13. For rash refer to Section 5.12.1. For diarrhoea refer to Section 5.12.2 and to Appendix 1	Maintain dose for 1 st and 2 nd appearance  Interrupt treatment until resolves to Grade 0-1, up to 14 days for 3 rd and 4 th appearance	1 st appearance-Maintain dose- No change 2 nd appearance- Maintain dose No change 3 rd appearance – Resume 100% or dose reduce to 1000mg/day 4 th appearance – Resume with a dose reduction to 1000mg/day.
Grade 3 – Any other event For Cardiac Ejection Fraction and interstitial pneumonitis AEs, refer to Section 5.12.3. For liver AE refer to Section 5.13. For rash refer to Section 5.12.1. For diarrhoea refer to Section 5.12.2 and to Appendix 1	Interrupt treatment until resolves to Grade 0-1, up to 14 days.	Any appearance-Resume 100% or Reduce dose to 1000mg permitted in consultation with GSK Medical Monitor.
Grade 4 For Cardiac Ejection Fraction and interstitial pneumonitis AEs, refer to Section 5.12.3 For liver AE refer to Section 5.13. For rash refer to Section 5.12.1. For diarrhoea refer to Section 5.12.2 and to Appendix 1	Interrupt treatment until resolves to Grade 0-1, up to 14 days.	Consult with GSK Medical Monitor to determine if in the best interest of the subject to continue at a dose reduction.

Toxicity grading system according to NCI-CTCAE V4.03

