**Table 11 Dose modification rules for capecitabine**

Toxicity NCI-CTCAE Grade	During Course of Therapy	Capecitabine Dose Change
Grade 1	Maintain dose	No change
Specific Events of Grade 2/3 Haematology ANCs $<1.5 \times 10^9/L$ Platelet count is $<100.0 \times 10^9/L$ Haemoglobin is $<9.0$ g/dL (after transfusion if needed) Chemistry For liver AE refer to Section 5.13. Serum Creatinine $\geq 1.5$ mg/dL. Calculated Creatinine Clearance $<40$ mL/mins (Appendix 6)	Interrupt treatment until resolved to Grade 0-1, up to 14 days.  If toxicity does not resolve, consult GSK Medical Monitor to determine if it is in the best interest of the subject to continue in the study.	1 st appearance -Resume at 100% or Resume at 75% (rounded to nearest 150mg) as clinically indicated 2 nd appearance Resume at 75% (rounded to nearest 150mg) 3 rd appearance-Resume at 50% of starting dose rounded to nearest 150mg) 4 th appearance-Discontinue permanently
Grade 2-Any other event For liver AE refer to Section 5.13. For diarrhoea refer to Section 5.12.2 and to Appendix 1	Interrupt treatment until resolved to Grade 0-1, up to 14 days.	1 st appearance -Resume at 100% or Resume at 75% (rounded to nearest 150mg) as clinically indicated 2 nd appearance Resume at 75% (rounded to nearest 150mg) 3 rd appearance-Resume at 50% of starting dose rounded to nearest 150mg) 4 th appearance-Discontinue permanently
Grade 3 – Any other event For liver AE refer to Section 5.13. For diarrhoea refer to Section 5.12.2 and to Appendix 1	Interrupt until resolves to Grade 0-1, up to 14 days.	1 st appearance-Resume 75% of starting dose (rounded to nearest 150mg) 2 nd appearance- Resume 50% of starting dose (rounded to nearest 150 mg) 3 rd appearance- Discontinue treatment permanently
Grade 4 For liver AE refer to Section 5.13. For diarrhoea refer to Section 5.12.2 and to Appendix 1	Interrupt until resolves to Grade 0-1, up to 14 days.	Consult GSK Medical Monitor to determine if it is in the best interest of the subject to continue at a dose level lower than the original capecitabine dose

Toxicity grading system according to NCI-CTCAE V4.03

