## 5.12. Guidelines for Events of Special Interest and Dose Modifications

The severity of AEs will be graded in accordance with the NCI CTCAE version 4.03. Guidelines for dose modifications and interruptions for management of common toxicities associated with the treatment with lapatinib and capecitabine are provided in this section. Any future changes made to this guidance will be communicated to the investigative sites in the form of a letter and the revised version will be included in the SPM.

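### Table 10 maintains lapatinib at a first or second Grade 2 hand-foot syndrome, where Section 5.12.4 stops it; a cross-reference is missing

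*Protocol*

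**What the plan says.** - **Protocol 5.12.4** grades hand-foot syndrome on "the capecitabine-specific toxicity rating scale shown in" Table 14. For capecitabine the instruction is to "follow the recommended dose modification guidelines for capecitabine described in Section 5.11". It then covers both drugs: "If Grade 2 or 3 hand-foot syndrome occurs, administration of lapatinib and capecitabine should be stopped until resolution to Grade 0-1". It gives no dose at which lapatinib restarts.
- **Protocol 5.10, Table 10 (lapatinib).** For Grade 2 events not otherwise listed, the entry for the first appearance reads "appearance-Maintain dose- No change". The second appearance is handled the same way, and interruption starts at the third. The row refers the reader elsewhere for ejection fraction and pneumonitis, liver events, rash and diarrhoea. Hand-foot syndrome and 5.12.4 are not mentioned. The footer reads "Toxicity grading system according to NCI-CTCAE V4.03".
- **Protocol 5.11, Table 11 (capecitabine).** For the same class of Grade 2 event: "Interrupt treatment until resolved to Grade 0-1, up to 14 days". It has the same grading footer as Table 10.
- **Routing.** Section 3.1 lists hand-foot syndrome as an event of special interest for capecitabine, names 5.12.4 for its management and 5.11 for capecitabine dosing. Section 5.1.1 sends lapatinib dose changes for toxicity to 5.10. Section 5.12 says of itself: "Guidelines for dose modifications and interruptions for management of common toxicities associated with the treatment with lapatinib and capecitabine are provided in this section".
- **Protocol 5.12.1.3 and 5.12.1.3.3** require lapatinib to be stopped for good at recurrent Grade 3 and at any Grade 4 dermatological reaction. Table 10 refers only rash to 5.12.1.

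**The concern.** A subject with a first Grade 2 hand-foot syndrome meets two opposite lapatinib instructions. A site that opens 5.12.4 holds the drug. A site that opens Table 10, where 5.1.1 sends it for lapatinib toxicity, continues it. Table 10 names its exceptions one by one, so a reader has reason to think that an event not named belongs in the catch-all row.

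Two things are at stake. A safety hold that the protocol states can be missed, and the same event can lead to different lapatinib exposure at different sites. The SAP summarises lapatinib interruptions with their reasons (2.7.1.2) and counts an incorrect dose as an important deviation category (2.3.2), so both outputs could mix the two rules.

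**Working it through.** The plan gives no figure on this point, so the check is a comparison of the texts followed by a rough size.

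**Step 1. Compare the rules.**

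| Event | 5.12.4 | Dose table | Agree? |
|---|---|---|---|
| Lapatinib, Grade 2, 1st or 2nd | stop until Grade 0-1 | Table 10: maintain | **No** |
| Lapatinib, Grade 2, 3rd or 4th | stop until Grade 0-1 | Table 10: interrupt | Yes |
| Lapatinib, Grade 3 | stop until Grade 0-1 | Table 10: interrupt | Yes |
| Capecitabine, Grade 2 | stop until Grade 0-1 | Table 11: interrupt | Yes |
| Capecitabine, Grade 3 | stop until Grade 0-1 | Table 11: interrupt | Yes |

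Only the first line conflicts, and what it concerns is a temporary hold.

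**Step 2. Which rule is intended?** Section 3.1 names 5.12.4 for this event. 5.12.4 names both drugs, while the Table 10 row is a residual category. The intended rule is therefore 5.12.4. Section 3.2 reads the same Table 10 row for Grade 2 diarrhoea as keeping lapatinib going at the first two occurrences, so the row does mean what it appears to say.

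**Step 3. How often could the text be met?** The input is protocol Table 2 (earlier trial, lapatinib with capecitabine, N = 210), row for palmar-plantar erythrodysesthesia (PPE).

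- Grades 1, 2 and 3: 27 + 67 + 36 = 130, which equals the row total. Each subject is therefore counted once, at worst grade.
- Worst grade 2: 67/210 = 31.9% (Clopper-Pearson 95% CI 25.7% to 38.7%).
- Applied to the 62 enrolled subjects (SAP Section 1): 62 × 0.319 = 19.8, about 20.
- Cross-check in Table 12 (n = 198): hand-foot syndrome 54% at any grade, 14% at Grade 3 and no Grade 4, so 54% − 14% = 40% had a worst grade of 1 or 2. A rate of 32% at worst Grade 2 fits within that.

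**Step 4. Size of the rash wording.** In Table 12 (lapatinib plus capecitabine), the only Grade 3 entry outside rash and hand-foot syndrome is skin infection, below 1%. Since 2/198 = 1.01%, that is at most one subject: 1/198 = 0.5%, or 62 × 0.005 = 0.3 subjects before any recurrence is required. The table reports no Grade 4 events.

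**The case against.** The best defence is that the protocol already routes the reader correctly. Section 3.1 sends hand-foot syndrome to 5.12.4 by name, 5.10 describes Table 10 as covering selected events, and an explicit instruction to stop both drugs should outweigh a residual row. This stands as far as intent goes. It does not remove the contradiction, because Section 3.1 gives no lapatinib dosing pointer for this event, 5.1.1 sends lapatinib toxicity to Table 10, and Table 10 gives the opposite instruction without an exception.

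A reader might infer more than the documents support:

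- **That continuing lapatinib while holding capecitabine is allowed.** Section 5.9 says "the dose of either agent may be adjusted independently of the other". That concerns dose adjustment. It does not authorise continuing a drug that 5.12.4 expressly stops.
- **That the two grading scales would sort subjects differently.** Table 14 and NCI-CTCAE are different scales, but the CTCAE criteria for hand-foot syndrome are not reproduced (Table 13 omits it), so no difference can be shown. The mismatch also affects Table 11 and is not special to Table 10.
- **That about 20 subjects were treated wrongly.** The count is of subjects who could meet the text. How many sites followed which rule is unknown.

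It is also fair to say that enrolment ended after the futility finding, so a correction reaches no new subjects.

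**Conclusion.** The contradiction is real and narrow: lapatinib at a first or second Grade 2 hand-foot syndrome. Section 5.12.4 is the intended rule and Table 10 departs from it. This is a patient-safety and treatment-consistency correction of minor severity.

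The 32% rests on three assumptions: that the earlier trial's rate carries over, that its follow-up is comparable with this study's 24 weeks, and that CTCAE Grade 2 corresponds to Table 14 Grade 2. The documents support none of these directly. The confidence interval reflects only the sampling error of the earlier trial.

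A reader might go on to infer a bias in the diarrhoea comparison, since lapatinib exposure can affect diarrhoea. The documents give no basis for that: both arms follow the same rules, and nothing suggests that sites would choose between them by arm.

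The gap for skin reactions other than rash is real but rare, and Section 3.1 already sends all dermatological events to 5.12.1 for management.

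**What to change.** **Main change.** In the Grade 2 and Grade 3 rows of Table 10 add: *For hand-foot syndrome refer to Section 5.12.4 (interrupt lapatinib at every Grade 2 or 3 occurrence until Grade 0-1, graded on Table 14).* The line should not set a restart dose, because 5.12.4 states none for lapatinib. If one is wanted, the sponsor's clinicians should supply it.

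**Optional and minor.** Change the rash pointer in Table 10 to: *For dermatological events other than hand-foot syndrome refer to Section 5.12.1.* The mandatory stops for recurrent Grade 3 and all Grade 4 skin reactions are then reached from the table. The exclusion is needed because Table 12 lists hand-foot syndrome among dermatological events, and the holding rule in 5.12.1.3.1 holds a Grade 2 reaction only if two weeks of management have not improved it. Without the exclusion, the change would create a new conflict with 5.12.4.

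**Cost.** A few words in Table 10, sent by the letter and Study Procedures Manual update that Section 5.12 already provides for. No new data and no change to the analysis. With enrolment closed, the benefit is for any subjects still on treatment, for reading the lapatinib interruption data, and for any reuse of the protocol text.

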Diarrhoea, nausea and vomiting, dermatological events, hepatobiliary, cardiovascular and respiratory events have been identified as events of special interest relating to lapatinib. Management of dermatological events, gastrointestinal events, and cardiovascular and respiratory events is described in Section 5.12.1, Section 5.12.2, and Section 5.12.3, respectively. Dose delay and dose reduction guidance for lapatinib related to these events and to hepatobiliary events is described in Section 5.10. If future changes are made to this guidance, formal documentation will be created and stored with the study file. Any changes will be communicated to the investigative sites in the form of a letter and the revised version of the AE management or dose modification guidelines will be included in the SPM.

Hand and foot syndrome has been identified as an event of special interest relating to capecitabine. Management of this event is described in further detail in Section 5.12.4. Dose delay and dose reduction guidance for capecitabine related to this event is described in Section 5.11. If future changes are made to this guidance, formal documentation will be created and stored with the study file. Any changes will be communicated to the investigative sites in the form of a letter and the revised version of the AE management or dose modification guidelines will be included in the SPM.

There are no events of special interest relating to octreotide [[Octreotide SPC](#)].

The GSK SRT will review safety data from this study on an ongoing basis. A formal review of safety data will be conducted after the first 60 subjects (approximately 30 in each treatment arm) have received at least 9 weeks of treatment with lapatinib and capecitabine; subsequent reviews will be conducted at least every 12 weeks, or more frequently if required. It is anticipated that the SRT will meet at least three times during the course of the study. There are no pre-defined stopping rules for this study.

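### For lapatinib at the first two appearances of Grade 2 hand-foot syndrome, Protocol Section 5.12.4 and Table 10 give opposite instructions, and no precedence is stated

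*Protocol*

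**What the plan says.** Protocol Section 5.12.4 is the only place that gives a lapatinib instruction for hand-foot syndrome by name. At Grade 2 or 3, "administration of lapatinib and capecitabine should be stopped until resolution to Grade 0-1". It does not distinguish first from later occurrences.

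Protocol Section 5.10, Table 10, sets the lapatinib rules by grade. Its row headed "Grade 2-Any other event" reads, for the first appearance, "appearance-Maintain dose- No change". The second appearance is treated the same way, and interruption begins only at the third. The row sends certain events elsewhere: ejection fraction and pneumonitis, liver, rash and diarrhoea. The nearest of these to hand-foot syndrome is "For rash refer to Section 5.12.1". There is no pointer to Section 5.12.4.

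Three other places bear on the point:

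- Section 3.1 names hand-foot syndrome as a capecitabine event of special interest, refers to Section 5.12.4 for its management, and adds "Dose delay and dose reduction guidance for capecitabine related to this event is described in Section 5.11". It gives no matching reference for lapatinib.
- Section 5.9 says "the dose of either agent may be adjusted independently of the other".
- Section 5.12.1.3.1 holds lapatinib for "a grade 2 dermatological reaction, which is unimproved after two-weeks of medical management". Table 12 in Section 5.12.1.2 lists hand-foot syndrome among the dermatological events.

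**The concern.** A site with a first or second Grade 2 hand-foot event cannot follow both Section 5.12.4 and Table 10 for lapatinib. One stops the drug and the other continues it. The specific section does not plainly override the table, because the table spells out its exceptions and leaves this one out.

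The event is common. In Table 2 (EGF100151, lapatinib with capecitabine), hand-foot syndrome, listed as PPE, is the most frequent Grade 2 event shown and ranks second to diarrhoea across all grades.

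What is at stake is the consistency of lapatinib dosing. Compliance with lapatinib and capecitabine is a secondary endpoint (Protocol Table 7), kept in the reduced list of SAP Table 1-3. SAP Section 2.4.1 derives it as cumulative actual dose over cumulative planned dose. SAP Section 2.6.1.4 says inference about octreotide will be drawn from it. If lapatinib is interrupted or continued according to which page a site consulted, part of the variation in exposure comes from the wording and not from the patients. Lapatinib also causes diarrhoea, so uneven interruption could in principle reach the 9-week endpoint.

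**Working it through.** **1. The instructions side by side**

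| Situation | Section 5.12.4 | Dose table | Agree? |
|---|---|---|---|
| Lapatinib, Grade 2, 1st or 2nd appearance | Stop until Grade 0-1 | Table 10: maintain dose | No |
| Lapatinib, Grade 2, 3rd or 4th appearance | Stop until Grade 0-1 | Table 10: interrupt | Yes, on interrupting |
| Lapatinib, Grade 3 | Stop until Grade 0-1 | Table 10: interrupt | Yes, on interrupting |
| Capecitabine, Grade 2 or 3 | Stop until Grade 0-1 | Table 11: interrupt | Yes, on interrupting |

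Only the first line conflicts. If hand-foot syndrome is treated as a dermatological reaction, as its place in Table 12 allows, Section 5.12.1.3.1 gives a third answer for that line: hold lapatinib only after two weeks of management without improvement.

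**2. Does any text settle precedence?**

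None was found. Section 5.1.1 sends management of treatment-related toxicities under lapatinib to Section 5.10. Section 3.1 likewise names Section 5.10 for lapatinib dose delays and reductions. Section 5.9 lets each drug be adjusted separately, so holding capecitabine does not by itself mean holding lapatinib.

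**3. Frequency in Table 2 (N = 210)**

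- Grade 2: 67/210 = 31.9% (stated 32%).
- All grades: 130/210 = 61.9% (stated 62%).
- Row sum: 27 + 67 + 36 = 130, so each subject appears to be counted once, at maximum grade.
- Diarrhoea for comparison: Grade 2, 48/210 = 22.9%; all grades, 145/210 = 69.0%.

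The stated figures reproduce.

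**4. How many subjects could meet the conflict**

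Exact (Clopper-Pearson) 95% interval for 67/210: the lower limit is the 2.5% quantile of Beta(67, 144), 25.7%. The upper limit is the 97.5% quantile of Beta(68, 143), 38.7%.

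Expected number = subjects × rate:

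- Planned 140: 140 × 67/210 = 44.7, about 45. Range 140 × 0.2566 = 35.9 to 140 × 0.3867 = 54.1, so 36 to 54.
- Enrolled 62 (SAP Section 1): 62 × 67/210 = 19.8, about 20. Range 62 × 0.2566 = 15.9 to 62 × 0.3867 = 24.0, so 16 to 24.

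The ranges carry only the sampling error of the EGF100151 rate. They do not cover differences in follow-up or grading scale between the studies.

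**The case against.** The best defence is that the specific text governs. Section 5.12.4 names the event, both grades and both drugs, whereas the opposing instruction is inferred from a catch-all row in a table that Section 5.10 describes as covering selected adverse events. Section 5.12 presents itself as the place for dose guidance on common toxicities, and Section 3.1 sends the reader to 5.12.4. Many sites would probably land there. This stands to the extent that divergence between sites is a possibility and not a certainty. It does not remove the contradiction, because Table 10 names its exceptions without this one and Section 5.1.1 points lapatinib toxicity back to Section 5.10.

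A reader might infer that the primary comparison is biased. The documents do not support that. Both arms work from the same text and nothing links octreotide to hand-foot syndrome, so the expected result is mainly non-differential noise. The study is open label, so differential application is conceivable, but there is no evidence of it. Timing also weakens the inference. In EGF111438 the median onset of diarrhoea was 12 days and 55% of affected subjects had onset by day 14. Later lapatinib interruptions could not change those first onsets, and no onset times for hand-foot syndrome are given.

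A reader might also take 32% as the share of this trial's subjects affected, or affected within 9 weeks. Table 2 covers another study's follow-up, and the documents do not show that it used the capecitabine-specific scale of Table 14. Subjects whose maximum was Grade 3 may also have passed through Grade 2, which would push the count the other way.

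Finally, compliance is only summarised, with no test planned, and enrolment stopped for futility after 62 patients. Both points limit the practical consequence.

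**Conclusion.** The point holds as an internal inconsistency of limited scope: lapatinib, Grade 2 hand-foot syndrome, first and second appearance. Section 5.12.4 and Table 10 cannot both be followed, no precedence is stated, and the dermatological holding rule leaves a third reading open. It should not be read as extending to capecitabine, or to Grade 3 interruption under Table 10.

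Sites may interrupt lapatinib differently for the same event. The likely consequence is added noise in lapatinib exposure and in a descriptive compliance summary. An effect on 9-week diarrhoea cannot be ruled out, nor can it be sized from the documents.

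The counts of about 45 of 140 planned or about 20 of 62 enrolled rest on carrying over the EGF100151 Grade 2 rate. They show that the situation would not be rare; they do not measure a distortion in any result.

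**What to change.** Reconcile Section 5.12.4, Table 10 and Section 5.12.1.3.1 so that one lapatinib instruction applies to Grade 2 hand-foot syndrome at each appearance. State whether hand-foot syndrome falls under the dermatological rules. Add hand-foot syndrome, with its governing section, to the cross-references in Table 10. Which clinical rule is right is for the sponsor's clinical team to decide.

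The cost is protocol wording and a letter to sites, a route that Section 5.12 already provides for changes to this guidance. With enrolment closed there is little prospective gain in this trial. A sentence beside the compliance summary in the study report, noting that the lapatinib instruction for this event was ambiguous, would cost almost nothing.
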